### 12.3.1 Primary Analyses

The modified Intent-to-Treat (mITT) population will be used for the primary analyses.

The primary analysis variables are:

- Schiff sensitivity score at Day 0 (Baseline), Day 3, Weeks 2, 4 and 8;
- Tactile threshold (g) at Days 0 (Baseline), Day 3, Weeks 2, 4 and 8;
- Number of sensitive teeth (Schiff sensitivity score  $\geq 1$ ) at Day 0 (Baseline), Day 3, Weeks 2, 4 and 8.

Schiff sensitivity score is derived as the average score of the two test teeth; tactile threshold (g) is derived in the same way. Summary statistics (mean, median, SE, SD, minimum,

Property of GSK Consumer Healthcare - Confidential

May not be used, divulged, published or otherwise disclosed without the consent of  
 GSKCH

CCI

Clinical Protocol Template v7.0

Page 79 of 100

maximum) will be presented for each outcome variable at each assessment time point. Raw means ( $\pm$  SE) of Schiff sensitivity score and tactile threshold (g) and the number of sensitive teeth at each timepoint will be plotted by product group.

### **12.3.2 Secondary Analyses**

Summary statistics (mean, median, SE, SD, minimum, maximum) will be presented for each secondary analysis variable by product group at each assessment time point, including Baseline assessments. Raw means ( $\pm$  SE) at each timepoint will be plotted by product group.

#### **Change from Baseline in Schiff sensitivity score at Day 3, Weeks 2, 4 and 8**

The Schiff sensitivity score is derived as the average score of the two test teeth. The change from Baseline is derived for the individual teeth first before calculating the average change of the two test teeth. The change in Schiff sensitivity score will be analysed at each time point using an ANCOVA model which will include product as a factor and Baseline Schiff sensitivity score as a covariate. Note that since the Baseline Schiff sensitivity score will be included as a covariate, the Baseline Schiff stratification value will not be included in the model.

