### **8.1.6 Screening Procedures**

The following procedures will be completed, and data recorded in the eCRF.

- Review the oral care products the subject is currently using (subject will provide the names of their current oral care products) to confirm they do not contain any ingredients intended for treating sensitive teeth.
- Female subjects of child-bearing potential only complete a UPT.
- Clinical examiner completes an OST examination as described in Section 9.3.1.
- Clinical examiner completes an OHT examination as described in Section 9.3.2.
- Clinical examiner completes eligible teeth assessments for incisors, canines and pre-molars, including dentition exclusions and assessments of EAR, MGI and tooth mobility as described in Section 5.3, Section 9.1.1, Section 9.1.2 and Section 9.1.3 respectively.
- Clinical examiner assesses the sensitivity of each tooth that meets the above eligibility criteria, first to a tactile stimulus and then to an evaporative (air) stimulus, as described in Section 9.1.4 and Section 9.1.5 respectively. Evaporative (air) sensitivity will only be assessed for teeth with a qualifying tactile threshold of  $\leq 20$  g. The examiner will allow at least 5 minutes between the completion of the tactile assessments and the start the evaporative (air) assessments.

Property of GSK Consumer Healthcare - Confidential

May not be used, divulged, published or otherwise disclosed without the consent of  
 GSKCH

CCI

Clinical Protocol Template v7.0

Page 50 of 100

To facilitate subject flow, clinical assessments may be recorded on a paper score sheet (source document) and later transcribed into the eCRF.

The same examiner will be responsible for completing both sensitivity measures (tactile and evaporative (air) sensitivity) for the duration of the study.

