### **12 STATISTICAL CONSIDERATIONS AND DATA ANALYSES**

#### **12.1 Sample Size Determination**

No formal sample size has been produced for this PoP clinical study to investigate changes in sensitivity measures (Schiff sensitivity score, tactile threshold and number of sensitive teeth) over time with twice-daily use of a novel combination toothpaste. Based on previous, similar GSK CH studies evaluating the sensitivity protection provided by daily-use toothpastes, approximately 30 evaluable subjects per product group is considered sufficient to provide reliable estimates of performance for the purposes of this study and to aid in the design of future clinical studies. Approximately 120 subjects will be randomised to study product.

From a previous, similar GSK CH study (GSKCH Clinical Study 209723, 2020), change in Schiff sensitivity score at Week 8 had an SD of 0.7 units and the degree of variability (SD) in the test and control groups remained roughly consistent with each other over time. A similar trend was observed for the tactile threshold and number of sensitive teeth endpoints.

A sample size of 30 evaluable subjects per product group is expected to provide 95% CIs with a width of  $\pm 0.261$  units for the Schiff sensitivity score. This level of precision is considered sufficient for the purposes of this study. Approximately 120 subjects will be randomised to study treatment.

Property of GSK Consumer Healthcare - Confidential

May not be used, divulged, published or otherwise disclosed without the consent of  
GSKCH

CCI

Clinical Protocol Template v7.0

Page 78 of 100

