#### **Change from Baseline in tactile threshold (g) at Day 3, Weeks 2, 4 and 8**

Tactile threshold (g) and change from Baseline will be derived as for the Schiff sensitivity score. The change in tactile threshold (g) will be analysed at each time point using an ANCOVA model with product and Baseline Schiff stratification included as factors and Baseline tactile threshold included as a covariate.

For both Change from Baseline in Schiff sensitivity score and Change from Baseline in tactile threshold, using the above models, adjusted mean change from Baseline, along with 95% CIs will be reported by product group. P-values testing for non-zero change from Baseline will also be presented for each product group. Mean difference between product groups, 95% CIs and p-values will also be provided. Significance testing will be conducted at the two-sided 5% significance level; no adjustment for multiple comparisons will be made.

Property of GSK Consumer Healthcare - Confidential

May not be used, divulged, published or otherwise disclosed without the consent of  
 GSKCH

CCI

Clinical Protocol Template v7.0

Page 80 of 100

In each case, the assumptions of the ANCOVA model will be investigated. An appropriate data transformation or non-parametric method may be performed in case of strong model violations.

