4.4.2.1.2 Statistical Hypothesis, Model and Method of Analysis

Study product differences will be tested under the null hypothesis:

- H_0 : there is no treatment difference
- H_1 : there is a treatment difference

The following study product comparisons will be analyzed:

- Test product versus negative control
- Test product versus comparator 1
- Test product versus comparator 2

Change in Schiff sensitivity score at Day 3, Weeks 2, 4, and 8 will be analyzed using an Analysis of Covariance (ANCOVA) model which will include study product as a factor and baseline Schiff sensitivity score as a covariate. Since the baseline Schiff sensitivity score will be included as a covariate, the baseline Schiff stratification value will not be included in the model.

Using the above model, adjusted mean change from baseline, along with 95% CIs will be reported by study product group. P-values testing for non-zero change from baseline will be presented for both study product groups. Mean difference between study product groups, 95% CIs and p-values will be provided for Schiff sensitivity score in Table 14.2.2.4.1. Significance

3% PVM/MA + 5% KNO₃ Toothpaste
218220

testing will be conducted at the two-sided 5% significance level; no adjustment for multiple comparisons will be made.

The assumption of normality and homogeneity of variance in the ANCOVA model will be investigated, and if violated, an appropriate data transformation or non-parametric method, for example, the van Elteren test, adjusting for baseline Schiff stratification, will be performed.

4.4.2.2 Secondary Efficacy Variable 2

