4.4.2.2.2 Statistical Hypothesis, Model and Method of Analysis

Study product differences will be tested under the null hypothesis:

- H_0 : there is no treatment difference versus the alternate hypothesis
- H_1 : there is a treatment difference

The following study product comparisons will be analyzed:

- Test product versus negative control
- Test product versus comparator 1
- Test product versus comparator 2

Change from baseline in tactile threshold (g) will be analyzed at Day 3, Weeks 2, 4, and 8 using an ANCOVA model with study product and baseline Schiff stratification included as factors and baseline tactile threshold (g) included as a covariate.

Using the above model, adjusted mean change from baseline, along with 95% CIs will be reported by study product group. The adjusted means will be derived using weighted model effects for the baseline Schiff stratification which are proportional to the split between strata observed in the data. P-values testing for non-zero change from baseline will be presented for both study product groups. Mean difference between study product groups, 95% CIs and p-values will be provided for tactile threshold (g) in Table 14.2.2.4.2. Significance testing will be conducted at the two-sided 5% significance level; no adjustment for multiple comparisons will be made.

3% PVM/MA + 5% KNO₃ Toothpaste
218220

The assumption of normality and homogeneity of variance in the ANCOVA model will be investigated, and if violated, an appropriate data transformation or non-parametric method, for example, the van Elteren test, adjusting for baseline Schiff stratification, will be performed.

4.4.2.3 Secondary Efficacy Variable 3

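### Both ANCOVAs could also adjust for the Screening reading of the same two test teeth: an optional and probably small gain in precision for the secondary comparisons

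*Protocol*

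**What the plan says.** In protocol 12.3.2, change in Schiff score is analysed at each visit "using an ANCOVA model which will include product as a factor and Baseline Schiff sensitivity score as a covariate". Change in tactile threshold uses an "ANCOVA model with product and Baseline Schiff stratification included as factors and Baseline tactile threshold included as a covariate". SAP 4.4.2.1.2 has the same Schiff analysis, a "model which will include study product as a factor and baseline Schiff sensitivity score as a covariate", and SAP 4.4.2.2.2 has the same tactile analysis, an "ANCOVA model with study product and baseline Schiff stratification included as factors and baseline tactile threshold (g) included as a covariate". SAP 3.1 defines baseline as the Day 0 value for all endpoints, so Screening does not enter through that definition either.

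The Screening readings exist. Protocol 8.1.6, whose results go into the eCRF, states: "Clinical examiner assesses the sensitivity of each tooth that meets the above eligibility criteria, first to a tactile stimulus", followed by the air stimulus for teeth that qualify on tactile threshold. Under protocol 5.2 (criterion 7) and 9.2.5, a tooth can be a test tooth only if it qualified on both measures at both Screening and Baseline. Protocol 4.1 and 8.1.6 have one examiner perform both measures throughout. Every subject randomised in line with the criteria therefore has a Screening Schiff score and tactile threshold for the same two teeth.

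On inference, the protocol says: "Significance testing will be conducted at the two-sided 5% significance level; no adjustment for multiple comparisons will be made". On size, it says: "No formal sample size has been produced for this PoP clinical study". Precision rests on an earlier study in which "change in Schiff sensitivity score at Week 8 had an SD of 0.7 units".

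**The concern.** The Day 0 covariate is coarse. A qualifying tooth scores Schiff 2 or 3, so the two-tooth mean can only be 2, 2.5 or 3. Tactile force is capped at 20 g at Baseline and rises in 10 g steps, so that mean can only be 10, 15 or 20 g. A second reading of the same teeth, by the same examiner with the same two tests, may separate subjects whom a three-level value cannot.

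At stake is the precision of the comparisons of the Test product with its two components and the negative control: 2 measures × 4 visits × 3 comparisons = 24 contrasts. Protocol 4.2 describes the Test-versus-Comparator contrasts as of particular interest, and the results are meant to inform later studies. Because Screening precedes randomisation, adjusting for it cannot bias these contrasts.

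**Working it through.** **Inputs from the documents.** SD of change in Schiff at Week 8: 0.7. Evaluable subjects: 30 per arm, four arms (protocol 12.1). Two-sided 5%, no multiplicity adjustment (protocol 12.3.2). The 0.7 is the SD of raw change, not an ANCOVA residual SD, so using it as the residual SD gives an upper bound on width.

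**Input that the documents do not give.** The partial correlation r of the Screening value with the outcome, given the terms already in the model. It is assumed below and shown as a range.

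**Step 1: the plan's own figure.** Single-arm half-width = t(0.975, 29) × 0.7/√30 = 2.045 × 0.1278 = 0.261. This reproduces the stated ±0.261, which is for one arm and not for a difference between arms.

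**Step 2: a product difference under the planned Schiff model.** Residual df = 120 − 4 − 1 = 115. Half-width = t(0.975, 115) × 0.7 × √(2/30) = 1.981 × 0.1807 = **±0.358**.

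**Step 3: add Screening Schiff.** The residual SD is multiplied by √(1 − r²) and the df become 114. The equivalent size per arm is 30/(1 − r²).

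| Assumed r | Half-width | Change | Equivalent n per arm |
|---|---|---|---|
| 0 | ±0.358 | none | 30.0 |
| 0.1 | ±0.356 | −0.5% | 30.3 |
| 0.2 | ±0.351 | −2.0% | 31.2 |
| 0.3 | ±0.342 | −4.6% | 33.0 |
| 0.4 | ±0.328 | −8.3% | 35.7 |

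Estimating one more slope costs about 1/115 of the variance on average, or √(1 + 1/115) − 1 = 0.4% of width. The table leaves this out. Break-even is therefore near |r| = 1/√115 = 0.093, and at r = 0.1 the net gain is almost nil.

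**Step 4: which r is plausible?** If all visits were equally correlated at ρ, with no truncation, then r = ρ/(1 + ρ). For ρ = 0.3, 0.5 and 0.7 this gives r = 0.23, 0.33 and 0.41, and a narrowing of 2.7%, 5.7% and 8.9%. Eligibility truncates both pre-treatment readings, so these figures are likely to be too favourable.

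**Step 5: simulation with the eligibility rules applied.** Assumed latent tooth sensitivity: subject variance 0.6, tooth variance 0.4, visit noise variance 0.2, 0.5 or 1.0. Assumed response: mean 0.7 or 1.5, SD 0.4, 0.8 or 1.2. The latent value was cut into Schiff 0-3 and into 10 g tactile steps, and two teeth were taken from those that qualified on both measures at both visits. Across the 18 combinations:

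- The same-measure Screening covariate cut the standard error by 1.0-5.1% for Schiff and 0.6-3.6% for tactile.
- In the five combinations with a Schiff change SD of 0.68-0.74, close to the plan's 0.7, the cut was 2.1-2.5% for Schiff and 1.3-1.9% for tactile.
- Allowing extra noise in the Schiff Screening reading brings the lower end to about zero.

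Applied to Step 2, the best Schiff case is 0.358 × (1 − 0.051) = ±0.340. The cases close to SD 0.7 give about 0.358 × (1 − 0.025) = ±0.349 to 0.358 × (1 − 0.021) = ±0.350.

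**The case against.** The strongest reply is that nothing here is wrong. ANCOVA on change with the Day 0 value as covariate is standard and unbiased, the protocol and SAP agree, and baseline is defined explicitly. That stands in full.

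The second reply is that Screening is not an equivalent repeat of Day 0, and this also stands:

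- It is truncated in the same way: Schiff 2 or 3 per tooth, tactile capped at 20 g.
- It comes before the 2-4 week acclimatisation on a common toothpaste, which was included to limit placebo effects and standardise hygiene (protocol 4.1).
- The 8-hour hygiene and 4-hour food and drink restrictions in protocol 5.5.1 and 5.5.2 run from Visit 2 to Visit 6, so they do not cover Screening.

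Third, no decision turns on a few percent of width. The primary analysis is descriptive (SAP 4.4.1.2), there is no formal success criterion (protocol section 3), and the comparisons are secondary. Even the best case is 0.358 − 0.340 = 0.018 Schiff units, on a two-tooth mean that moves in steps of 0.5. This lowers the priority. It does not remove the option of using data already collected.

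A reader might go further and infer that leaving Screening out widens every Test-versus-comparator interval. The documents do not support that. It needs a partial correlation that they do not report, and below about 0.09 there is nothing to gain. A reader might also infer that the covariate would be complete for all randomised subjects. That holds only for subjects without a relevant eligibility deviation. The mITT population (SAP 4.1.3) does not exclude a subject randomised in error without a Screening reading.

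**Conclusion.** The point holds as an optional efficiency improvement. Both planned models are sound, and both leave unused a pre-randomisation reading of the same teeth. The expected gain is small: roughly 0-5% narrower product-difference intervals, or about 0-3 extra subjects per arm in effect. At a Schiff SD of 0.7 and 30 per arm, the half-width goes from about ±0.358 to about ±0.34 at best, and more likely to about ±0.35.

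The upper part of the range rests on assumed variances and on Screening behaving like a repeat of Day 0. The differences in conditions at Screening could bring the gain close to zero. The planned analysis is neither biased nor invalid for lack of this covariate.

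**What to change.** Before unblinding, amend SAP 4.4.2.1.2 and 4.4.2.2.2 to add one covariate each, taken as the mean over the same two test teeth (not all eligible teeth): Screening Schiff score in the Schiff model, Screening tactile threshold in the tactile model. Keep Day 0 as the baseline for change and leave all other terms as they are. Record the addition in SAP section 5, which now declares no change from protocol version 2.0, and align protocol 12.3.2 if it is amended again.

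The cost is one degree of freedom per model and a short SAP edit, with no new data or procedures. State in advance how a subject randomised in error without a Screening reading is handled, since the no-imputation rule (SAP 4.4.4) would otherwise drop that subject from the model. If the sponsor prefers the present models, they remain acceptable.

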#### **Change from Baseline in tactile threshold (g) at Day 3, Weeks 2, 4 and 8**

Tactile threshold (g) and change from Baseline will be derived as for the Schiff sensitivity score. The change in tactile threshold (g) will be analysed at each time point using an ANCOVA model with product and Baseline Schiff stratification included as factors and Baseline tactile threshold included as a covariate.

For both Change from Baseline in Schiff sensitivity score and Change from Baseline in tactile threshold, using the above models, adjusted mean change from Baseline, along with 95% CIs will be reported by product group. P-values testing for non-zero change from Baseline will also be presented for each product group. Mean difference between product groups, 95% CIs and p-values will also be provided. Significance testing will be conducted at the two-sided 5% significance level; no adjustment for multiple comparisons will be made.

Property of GSK Consumer Healthcare - Confidential

May not be used, divulged, published or otherwise disclosed without the consent of  
 GSKCH

CCI

Clinical Protocol Template v7.0

Page 80 of 100

In each case, the assumptions of the ANCOVA model will be investigated. An appropriate data transformation or non-parametric method may be performed in case of strong model violations.

### **Change from Baseline in DHEQ at Day 3, Weeks 2, 4 and 8**

The following DHEQ-15 endpoints will be reported:

- Responses to Questions 7, 8 and 9, DHEQ Section 1 (as separate questions);
- Total Score for Questions 1 to 15, DHEQ Section 2;
- Restrictions Domain (total score for Questions 1 to 3, DHEQ Section 2);
- Adaptation Domain (total score for Questions 4 to 6, DHEQ Section 2);
- Social Impact Domain (total score for Questions 7 to 9, DHEQ Section 2);
- Emotional Impact Domain (total score for Questions 10 to 12, DHEQ Section 2);
- Identity Domain (total score for Questions 13 to 15, DHEQ Section 2);
- Change from Baseline at Day 3, and Week 2, 4 and 8 for each DHEQ endpoint.

Summary statistics (mean, median, SE, SD, minimum, maximum) will be presented for Change from Baseline for each DHEQ endpoint by product group at each assessment time point.

### **Change from Baseline in Numeric Rating Scale (NRS) at Day 3, Weeks 2, 4 and 8**

Summary statistics (mean, median, SE, SD, minimum, maximum) will be presented for Change from Baseline in NRS by product group at each assessment time point.

#### **12.3.3 Safety Analyses**

The Safety population will be used for safety analyses. Safety analyses will be performed according to product received. All AEs will be reviewed by the Clinical Research Scientist, or designee, prior to database lock and unblinding and will be coded using the MedDRA. During this review stage, AEs will be further categorised as oral or non-oral. AEs will be listed and summarised by product received. SAEs will also be listed. AEs will be regarded as 'treatment' emergent if they occur on or after the first product use at the Baseline visit.

Property of GSK Consumer Healthcare - Confidential

May not be used, divulged, published or otherwise disclosed without the consent of  
 GSKCH

CCI

Clinical Protocol Template v7.0

Page 81 of 100

The following AEs tables will be produced, presented by product group:

- listing of all AEs (randomised subjects and non-randomised subjects);
- summary of AEs;
- treatment emergent AEs by Oral/Non-Oral and Preferred Term (PT);
- treatment emergent AEs by System Organ Class (SOC) and PT;
- treatment emergent treatment related AEs by Oral/Non-Oral and PT;
- listing of serious AEs (if there are no SAEs, a null listing will be produced; if there are more than 5 treatment emergent serious AEs (SAEs), a table will be produced in place of the listing by SOC and PT);
- non-serious treatment emergent AEs by SOC and PT (only produced if there are more than 5 SAEs).

The results of the OST and OHT examinations will be listed and the results of the OST examinations will be tabulated.

#### **12.3.4 Exclusion of Data from Analysis**

Exclusion of any data from the analyses will be determined during Blind Data Review (BDR) prior to database lock. Any reasons for exclusion from an analysis population will be listed, if applicable.

#### **12.3.5 Demographic and Baseline Characteristics**

Demographic and Baseline characteristics summaries will be produced for the mITT and safety populations.

Categorical demographic variables include gender, race, ethnicity, Baseline Schiff stratification score. These variables will be summarised by the number and percentage of subjects with each relevant characteristic in each product group. Age will be summarised by the mean, standard deviation, median, minimum and maximum values in each product group.

Property of GSK Consumer Healthcare - Confidential

May not be used, divulged, published or otherwise disclosed without the consent of  
 GSKCH

CCI

Clinical Protocol Template v7.0

Page 82 of 100

